10.2. Study Intervention Compliance

Define how adherence to the protocol (e.g., administration of study intervention, use of device,) will be assessed, and verified (if applicable, e.g., plasma assays, electronic monitoring devices, daily diaries).

The project is limited because we are enrolling only older adults from the community with T2D who carry a smartphone. In addition, given the significant commitment necessary to participate in the group sessions for the intervention group an attrition is an inherent potential issue. We will take several steps to minimize attrition including providing reimbursement and collecting multiple contact information (cell phone, home phone, email addresses) from the participants in order to remind them of the scheduled group sessions. We will also provide periodic updates to providers to remind them of the study and the importance of their support. The information gained from the pilot project will inform future interventions using mHealth tools toward community-dwelling older adults with T2D.

10.3. Permitted Concomitant Therapy

This section should be consistent with the medication restrictions in the inclusion/exclusion criteria previously listed. Describe how allowed concomitant therapy might affect the outcome (e.g., drug-drug interaction, direct effects on the study endpoints).

N/A

10.4. Rescue Medicine

List all medications, treatments, and/or procedures that may be provided during the study for "rescue therapy" and relevant instructions.

 \boxtimes N/A, no rescue medicine

11. Study Intervention Discontinuation

11.1. Discontinuation of Study Intervention

Describe the criteria for discontinuing the study intervention (e.g., halting rules), including any monitoring test(s) and associated clinical decision point(s). Include reasons for temporary discontinuation of the study intervention (e.g., type and quantity of adverse events), clearly stating the length of time, if applicable, and describe the data to be collected at the time of study intervention discontinuation and approaches for restarting administration of or re-challenging with study intervention.

Participants will be allowed to discontinue from the study (mHealth+ group Intervention group) anytime.

11.2. Continued Follow-up Discontinuation of Study Intervention

Describe efforts that will be made to continue follow-up of participants who discontinue the study intervention, but remain in the study for follow-up, especially for safety and efficacy study endpoints (if applicable). Reasonable efforts must be made to undertake protocol-specified safety follow-up procedures to capture adverse events (AE), serious adverse events (SAE), and unanticipated problems involving risks to subjects or others (UPIRSOs).

Participants will be allowed to discontinue from the study (mHealth+ group Intervention group) anytime.

12. Statistical Considerations

12.1. Statistical Hypotheses

State the formal and testable null and alternative hypotheses for primary and key secondary endpoints, specifying the type of comparison (e.g., superiority, equivalence or non-inferiority, dose response) and time period for which each endpoint will be analyzed.

Behavioral lifestyle interventions using a smartphone for self-monitoring to improve frailty measurements, body weight, and glycemic control in overweight/obese older adults with T2D.

8

12.2. Sample Size Determination

Include number of participants to recruit, screen, and enroll to have adequate power to test the key hypotheses for the study. Provide all information needed to validate your calculations and judge the feasibility of enrolling and following the necessary number of participants.

Because the POCL model is complex and this is a pilot study, it is not practical or feasible to do a power analysis for the given experimental design but based on the work of Drs. [name] and [name], we believe at least 20 participants in the group (mHealth+ group Intervention group) are needed. The effect of the intervention on the change in frailty category and/or frailty scores will be used to calculate power and sample size estimation for a future, larger study.

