04.12.20: Due to COVID-19 and social distancing order, we are adding hemoglobin Hba1c home test for our eight participants who are finishing the study on April 20, 2020. We have called all 8 participants and informed them about Hba1c home testing kit that will be delivered to their house after the final and tenth virtual session on April 20, 2020. We have confirmed their home address over the phone to mail the kit. Participants have been informed that the PI will explain and run the test individually with all 8 participants. Our next study group will finish the study in 2nd week of June, 2020. We will continue to follow our study participants and provide monthly behavioral educational sessions

4

in the group intervention, virtually, until the social distancing order will be lifted. Our study is not enrolling any new participants at this time.

On April 20, 2020, eight participants will finish the study and we will collect focus group questions virtually. We will also collect their individual questionnaire virtually to collect end of study assessments. Once the social distancing order will lift, we will collect face to face blood test and frailty assessments.

10.20.20: we finished our participants (N=20) in the group intervention and due to COVID-19 restrictions we were not able to enroll our participants for the control group (Group B). We talked with IRB staff and study team and decided to stop enrolling participating for the control group (group B) as the risk was higher based on the inclusion criteria for our study participants than the benefits for the control participants. Modification due to Pandemic, forgoing control arm, and worked with the interventional participants still worked with the study data to meet study aim-the deviation related to COVID-19 did not impact subject rights, safety, welfare, or the overall integrity of the science of the study.

8. Protocol-Directed procedures, items, services or tests

List all procedures directed by the study plan - including items or services provided as part of routine or conventional care and those needed to diagnosis or treat research related complications.

Important Note – The protocol directed procedures listed must match those in the Schedule of Activities (attachment) 8.1. Drugs (trade and generic, dosage, route of administration)

N/A

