10.1. Measures to Minimize Bias: Randomization and Blinding

This section should contain a description of randomization and blinding procedures (if applicable to the study design). It should include a description or a table that describes how study participants will be assigned to study groups, without being so specific that blinding or randomization might be compromised. Plans for the maintenance of trial randomization codes and appropriate blinding for the study should be discussed. The timing and procedures for planned and unplanned breaking of randomization codes should be included. Include a statement regarding when unblinding may occur and who may unblind. Provide the criteria for breaking the study blind or participant code. Discuss the circumstances in which the blind would be broken for an individual or for all participants (e.g., for serious adverse evets (SAEs)). Indicate to whom the intentional and unintentional breaking of the blind should be reported.

The PI will not be blinded by the study mHealth+ group Intervention group and mHealth+ individual intervention group.

Participants (N=40) be randomized into two groups using a block randomization table to receive behavioral lifestyle educational intervention. Everyone will receive a baseline and end of study visits.

We divided our future participants into 4 groups (10 - (group A):10- (group A):10- (individual B):10 (individual B) and with the help of computer generated program, we will start our intervention group (Group A - n=20) first followed by our control group (Group B - n=20). (see updates dated below)

Participant in mHealth + group intervention (Group A) you will receive a total of 10 group sessions in 6-months. The group will receive 3 weekly classes in the first month and then bi-weekly classes for month 2-3, and three monthly session in month four, five, and six.

10.20.2020: we completed up to three face to face group intervention sessions (Group A) over WebEx due to COVID-19 restrictions.

10.20.20: we finished our participants (N=20) in the group intervention and due to COVID-19 restrictions we were not able to enroll our participants for the control group.

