After discussing with IRB person and mentors, we decided to not to enroll participants for the Group B due to highrisk for COVID-19. We were able to receive enough information from the Group A intervention participants and to finish enrolling participants for the pilot study. Modification due to Pandemic, forgoing control arm, and worked with the interventional participants still worked with the study data to meet study aim-the deviation related to COVID-19 did not impact subject rights, safety, welfare, or the overall integrity of the science of the study.

7

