12.3. Populations for Analyses

Clearly identify and describe the analysis datasets (e.g., which participants will be included in each).

The impact of the intervention on frailty status (non-frail, pre-frail, frail) and frailty score (0, 1, 2, 3, 4, or 5) over the 6month period (from baseline to follow-up) will be assessed by proportional odds cumulative logit (POCL) model to assess the log-odds of frailty as an indicator of being exposed to the intervention. The initial POCL model will adjust only for the baseline value of frailty status. A subsequent model will adjust for baseline age, sex, ethnic group, BMI, and Hba1c, to determine potential covariate interactions with the intervention. Continuous secondary outcomes including fasting glucose, Hba1c, and BMI will be assessed using linear regression with intervention, baseline frailty, sex, and ethnic group as categorical predictor variables and baseline age, BMI, and Hba1c as continuous predictor variables. The categorical outcomes SPPB and PROMIS scores will also be evaluated using the POCL model.

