12.4. Statistical Analyses

Include analysis of primary efficacy endpoints, secondary endpoints, safety analyses, and any planned interim analyses

The impact of the intervention on frailty status (non-frail, pre-frail, frail) and frailty score (0, 1, 2, 3, 4, or 5) over the 6month period (from baseline to follow-up) will be assessed by proportional odds cumulative logit (POCL) model to assess the log-odds of frailty as an indicator of being exposed to the intervention. The initial POCL model will adjust only for the baseline value of frailty status. A subsequent model will adjust for baseline age, sex, ethnic group, BMI, and Hba1c, to determine potential covariate interactions with the intervention. Continuous secondary outcomes including fasting glucose, Hba1c, and BMI will be assessed using linear regression with intervention, baseline frailty, sex, and ethnic group as categorical predictor variables and baseline age, BMI, and Hba1c as continuous predictor variables. The categorical outcomes SPPB and PROMIS scores will also be evaluated using the POCL model. Because the POCL model is complex and this is a pilot study, it is not practical or feasible to do a power analysis for the given experimental design but based on the work of Drs. [name] and [name], we believe at least 20 participants in the group (mHealth+ group Intervention group) are needed. The effect of the intervention on the change in frailty category and/or frailty scores will be used to calculate power and sample size estimation for a future, larger study.

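### With only Group A enrolled, the intervention terms in Sections 12.3 and 12.4 cannot be estimated, so the rule for sizing a future study has no between-arm effect to use

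*Combined protocol and SAP*

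**What the plan says.** - **Sizing rule (12.2, repeated in 12.4).** "The effect of the intervention on the change in frailty category and/or frailty scores will be used to calculate power and sample size estimation". The stated purpose is to plan a later and bigger trial. The sentence before it gives at least 20 participants in the group-intervention arm, as a judgement and without a power calculation.
- **Primary model (12.3, repeated in 12.4).** Frailty status (three categories) and frailty score (0 to 5) are analysed by a POCL model "to assess the log-odds of frailty as an indicator of being exposed to the intervention". The first model adjusts for baseline frailty status. A second adds age, sex, ethnic group, BMI and HbA1c "to determine potential covariate interactions with the intervention". SPPB and PROMIS scores also use POCL.
- **Secondary continuous outcomes (12.4).** Fasting glucose, HbA1c and BMI are analysed by "linear regression with intervention, baseline frailty, sex, and ethnic group as categorical predictor variables", with continuous baseline covariates.
- **What happened to the arms.** Section 7 planned 20 in Group A and 20 in Group B. Section 10.1 has Group A run first and Group B afterwards. The 10.20.20 updates in Sections 7 and 10.1 report that 20 Group A participants finished and that "due to COVID-19 restrictions we were not able to enroll our participants for the control group". Section 10.1 adds: "We were able to receive enough information from the Group A intervention participants".
- **Timing of the end-of-study frailty assessment.** The 04.12.20 update in Section 7 defers face-to-face blood tests and frailty assessments, for the eight participants finishing on April 20, 2020, until the distancing order is lifted.

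**The concern.** An exposure effect needs both exposed and unexposed participants, and this study has only exposed ones. The models in Section 12 nevertheless keep the intervention term, and the sizing rule still relies on an intervention effect.

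Group A's own change can be estimated, but it is a different quantity. It combines any effect of the intervention with the passage of time and with the pandemic. The protocol itself points to the pandemic: a focus group question added on 04.12.20 (Section 8.6) asks how the virus affected self-monitoring of diet, physical activity and diabetes management, and low physical activity is one of the five frailty criteria. For the eight participants with deferred assessments, the interval may also exceed six months.

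No participant is affected. At stake are how the pilot's frailty result is labelled, and whether a controlled trial planned from it would have its intended power.

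**Working it through.** **Step 1. Is there a figure to reproduce?** No. The 20 per group in Section 12.2 comes with no alpha, power, effect size or variance. The check is therefore one of estimability.

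**Step 2. Primary model.** For three frailty categories the POCL model has two thresholds. Add exposure and two indicators for baseline frailty (all three baseline categories assumed to occur), and the stacked design has 2 + 1 + 2 = 5 columns.

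| Participants | Columns | Rank |
|---|---|---|
| 20 in A, 20 in B (as planned) | 5 | 5 |
| 20 in A, 0 in B (as enrolled) | 5 | 4 |

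With Group A alone the exposure column is 1 in every row, which is the sum of the two threshold columns. Its coefficient has no unique value. The 0 to 5 score has more thresholds, but they again sum to a column of ones, so the result is the same.

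**Step 3. Interactions.** For any covariate x, the product x × exposure equals x × 1 = x. Each interaction duplicates its main effect, whichever interactions are chosen and however ethnic group is coded.

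**Step 4. Secondary regressions.** The intervention column equals the intercept. With an intercept, intervention and one covariate, Group A alone gives rank 2 of 3. Adding covariates does not remove the duplication.

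**Step 5. Is there another route to the effect?** Sections 12.2 to 12.4 give no time term, repeated-measures model or external comparator. Because Group A was run first and Group B was never started, there is no partial concurrent comparator.

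**Step 6. Illustration of the consequence if Group A's change were used as a between-arm effect.** The documents supply none of these inputs; all are assumed: two-sided 5%, 80% power, two equal arms, effects in SDs of change.

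- Sample size: n per arm = 2(1.96 + 0.8416)² / d². At d = 0.5 this is 62.8, so 63.
- True power: Φ(d_true × √(63/2) − 1.96), where d_true = 0.5 minus the comparator's own improvement.

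| Comparator's change | d_true | Power with 63 per arm | Needed per arm |
|---|---|---|---|
| Improves 0.2 SD | 0.3 | 39% | 175 |
| Improves 0.1 SD | 0.4 | 61% | 99 |
| None | 0.5 | 80% | 63 |
| Worsens 0.1 SD | 0.6 | 92% | 44 |
| Worsens 0.2 SD | 0.7 | 98% | 33 |

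Improvement in a similar comparator is plausible: the Group B planned in Section 7 was active, with an abbreviated lifestyle session, the same kind of self-monitoring, study materials and monthly calls. The calculation uses a mean difference whereas the planned primary model is ordinal, so it shows direction and rough scale only.

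**The case against.** **Effect may simply mean before-after change.** The sizing sentence speaks of change, Section 12.4 refers to the period from baseline to follow-up, and nothing says outright that the POCL coefficient will be carried into the sizing. The looser reading is open, but it does not rescue the text. Baseline frailty enters as a covariate and not as a repeated response, no time term is given, and intervention is a separate predictor. On this reading the rule is undefined for one arm, and the quantity still has no comparator.

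**Section 12 is not wholly a two-arm text.** This stands. The sample-size sentence names only the 20 participants in the group intervention, so a reader who infers that Section 12 ignores the dropped arm altogether goes too far. What was not revised for one arm is the models and the sizing rule.

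**The harm is conditional.** This also stands. A reader might infer from "We were able to receive enough information from the Group A intervention participants" that Group A's change will be used as the between-arm effect of the next trial. The documents do not show this: that sentence justifies ending enrolment and does not mention sizing, and no future design is stated.

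**Regression to the mean.** Section 8.6 admits participants whatever their frailty status, so there was no selection on the primary outcome. The point does not rest on it.

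**It is a pilot with a feasibility objective.** That lowers the stakes, but informing a larger study is the use that Section 12 itself gives to the frailty effect.

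**Conclusion.** The concern holds. With 20 exposed and no unexposed participants, the exposure term in the POCL models, its covariate interactions and the intervention term in the secondary regressions cannot be estimated. This follows from the constant exposure column alone and needs no assumption about covariates, effect sizes or missing data. The sizing rule in 12.2 and 12.4 is therefore left without a between-arm effect.

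The mis-sizing in Step 6 is a conditional illustration on assumed inputs. It can go either way: a future trial would be too small if its comparator improves and too large if it worsens. It does not measure an error the sponsor has made. The plan should be corrected because its stated analyses cannot be run and no single-arm analysis takes their place.

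**What to change.** **Sections 12.3 and 12.4.** Remove the intervention term and its interactions. Describe the analyses as within-group change from baseline to end of study, with 95% confidence intervals:

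- frailty category and score, SPPB and PROMIS: a paired ordinal method, for example the Wilcoxon signed-rank test, or a cumulative logit model with a time term and a participant effect;
- fasting glucose, HbA1c and BMI: paired mean change.

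Report the actual interval between assessments and flag those that were delayed.

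**Sections 12.2 and 12.4.** Replace the sentence ending "frailty category and/or frailty scores will be used to calculate power and sample size estimation for a future, larger study" with: *Group A's change in frailty category and score will be reported as an uncontrolled change and will not be used as the between-arm effect for a future trial. The pilot will supply the distribution of frailty categories, the SD of the frailty score and of its change, and retention, each with a 95% CI. The target difference or odds ratio for a future controlled trial will be justified separately.*

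**Cost.** No new data or participants are needed, but this is more than a change of wording: a replacement analysis must be specified and the target effect needs another source. The pilot can no longer be described as estimating the intervention's effect on frailty.

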12.3. Populations for Analyses

Clearly identify and describe the analysis datasets (e.g., which participants will be included in each).

The impact of the intervention on frailty status (non-frail, pre-frail, frail) and frailty score (0, 1, 2, 3, 4, or 5) over the 6month period (from baseline to follow-up) will be assessed by proportional odds cumulative logit (POCL) model to assess the log-odds of frailty as an indicator of being exposed to the intervention. The initial POCL model will adjust only for the baseline value of frailty status. A subsequent model will adjust for baseline age, sex, ethnic group, BMI, and Hba1c, to determine potential covariate interactions with the intervention. Continuous secondary outcomes including fasting glucose, Hba1c, and BMI will be assessed using linear regression with intervention, baseline frailty, sex, and ethnic group as categorical predictor variables and baseline age, BMI, and Hba1c as continuous predictor variables. The categorical outcomes SPPB and PROMIS scores will also be evaluated using the POCL model.

12.4. Statistical Analyses

Include analysis of primary efficacy endpoints, secondary endpoints, safety analyses, and any planned interim analyses

The impact of the intervention on frailty status (non-frail, pre-frail, frail) and frailty score (0, 1, 2, 3, 4, or 5) over the 6month period (from baseline to follow-up) will be assessed by proportional odds cumulative logit (POCL) model to assess the log-odds of frailty as an indicator of being exposed to the intervention. The initial POCL model will adjust only for the baseline value of frailty status. A subsequent model will adjust for baseline age, sex, ethnic group, BMI, and Hba1c, to determine potential covariate interactions with the intervention. Continuous secondary outcomes including fasting glucose, Hba1c, and BMI will be assessed using linear regression with intervention, baseline frailty, sex, and ethnic group as categorical predictor variables and baseline age, BMI, and Hba1c as continuous predictor variables. The categorical outcomes SPPB and PROMIS scores will also be evaluated using the POCL model. Because the POCL model is complex and this is a pilot study, it is not practical or feasible to do a power analysis for the given experimental design but based on the work of Drs. [name] and [name], we believe at least 20 participants in the group (mHealth+ group Intervention group) are needed. The effect of the intervention on the change in frailty category and/or frailty scores will be used to calculate power and sample size estimation for a future, larger study.

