8.6. Other Research Procedures (e.g., other safety and efficacy assessments.)

Frailty assessment: We will conduct the assessment at the baseline and then at the end of the study. Frailty is defined as the presence of $\geq 3/5$ of characteristics 1) self-reported unintentional weight loss of ≥ 10 pounds in last year, 2) self-reported exhaustion, 3) low physical activity based on the Minnesota Leisure Time Physical Activity Questionnaire, 4) weak handgrip, 5) and slowness on a 10-foot walk at the usual pace. These measures have been standardized in SALSA study ^{7,21} and will be used in this study. Pre-frailty is defined as 1 or 2 of these characteristics and Non-frailty is defined as the presence of 0 characteristics. As a measure of lower extremity function, we will use the Short Physical Performance Battery (SPPB).²² All participants regardless of frailty status are eligible for study inclusion.

5

History and Physical Assessment: We will document participants' medical history regarding his/her diagnosis of T2D, length time having T2D, and use of any glucose-lowering medications and/or insulin. Height, weight, waist circumference, and vital signs (blood pressure, heart rate, temperature, and respiration) will be measured. Patient-Reported Outcomes Measurement Information System (PROMIS): PROMIS-Global Health (GH) and PROMIS-57 questionnaires, and a single-item Binge eating question will be completed by all participants at the baseline and end of study visit. In addition, all participant will complete focus group questionnaires at the end of study visit. For this study, we will recruit 20 participants for group intervention. All participants will receive a baseline and end of study visit. Participants in the group intervention will receive 10 behavioral education sessions. We will have 4-8 participants in each group intervention The focus group will be conducted at the end of study visit and procedures (session 10, visit 11) for the group intervention population. Participants will be informed in the consent and once

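### With Group B never enrolled, the intervention and interaction terms in Sections 12.3 and 12.4 cannot be estimated, and no analysis of within-person change in frailty is specified in their place

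*Combined protocol and SAP*

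**What the plan says.** Section 7 plans 40 participants, 20 in Group A (group sessions) and 20 in Group B (abbreviated individual delivery). Its 10.20.20 update reports that Group A finished with 20 and that the team "decided to stop enrolling participating for the control group (group B"). The update of the same date in Section 10.1 confirms that "we were not able to enroll our participants for the control group". Both sections go on to say that the study aim can be met from Group A and that the science was not compromised.

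The form's footer carries the same October 2020 amendment date, so Section 12 is current text. Sections 12.3 and 12.4 contain the same analysis paragraph:

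- Frailty status and score are analysed with a POCL model "to assess the log-odds of frailty as an indicator of being exposed to the intervention", first adjusting only for baseline frailty status.
- A second model adds baseline age, sex, ethnic group, BMI and HbA1c "to determine potential covariate interactions with the intervention".
- Fasting glucose, HbA1c and BMI are analysed by "linear regression with intervention, baseline frailty, sex, and ethnic group as categorical predictor variables", with baseline age, BMI and HbA1c as continuous predictors.
- SPPB and PROMIS scores also go through the POCL model.

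Section 12.2, repeated in 12.4, gives the intended use in planning a later trial: "The effect of the intervention on the change in frailty category and/or frailty scores will be used to calculate power and sample size estimation".

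**The concern.** Every effect named in Section 12.4 is a coefficient on exposure to the intervention, or an interaction with it. All participants with data were exposed, so there is no contrast from which to estimate it. Section 3 names frailty as the primary outcome, and the frailty effect is what the pilot is meant to hand on.

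An analyst who follows the text will get either an error or a silently dropped term. What remains is the follow-up distribution given baseline covariates, which contains no intervention effect but could be reported as one. The analyst must then choose a replacement measure after Group A has finished, with nothing in the plan to constrain the choice. If uncontrolled before-to-after change is carried forward as the intervention effect, any change that would have happened anyway is counted as effect in the next trial's sample size.

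**Working it through.** **Inputs.** Group A = 20 and Group B = 0 (Sections 7 and 10.1, 10.20.20 updates). Predictors are from Section 12.4. Frailty has one baseline and one end-of-study assessment per person (Section 8.6). The plan's figure of at least 20 in Group A (Section 12.2) cannot be reproduced, because no alpha, power, effect size or SD is given.

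**1. Algebra.** Write the POCL as logit P(Y ≤ j) = α_j − (βT + γ′B), with T the intervention indicator and B the baseline terms. If T = 1 for everyone, this is (α_j − β) − γ′B. Only the differences α_j − β are identified: adding any constant to β and to every threshold leaves the likelihood unchanged. For an interaction, T × covariate = covariate, so its coefficient cannot be separated from the main effect. The same holds in the linear regressions, where T equals the intercept column.

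**2. Rank check.** Simulated covariates, with three baseline frailty levels (2 dummies) and two ethnic groups, both assumptions. The constant stands for the thresholds.

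| Model | Columns | Rank, 20 + 20 | Rank, 20 + 0 | Lost |
|---|---|---|---|---|
| Initial POCL: constant, intervention, 2 frailty dummies | 4 | 4 | 3 | 1 |
| Linear regression: the above plus sex, ethnic group, age, BMI, HbA1c | 9 | 9 | 8 | 1 |
| Subsequent POCL: the above (baseline frailty kept) plus 5 interactions | 14 | 14 | 8 | 6 |

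With three ethnic groups the last two rows at 20 + 0 become 9 of 10 and 9 of 16; at 20 + 20 they are full rank.

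**3. Likelihood check.** On illustrative data (n = 20), setting the intervention coefficient to −5, −1, 0, 1 and 5 and shifting both thresholds by the same amount gave a log-likelihood of −14.5479 each time. The value means nothing in itself; that it does not move is the point. One standard ordinal routine (statsmodels OrderedModel) refuses the all-exposed design because it contains a constant.

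**4. What a single-arm analysis can deliver.** The 95% CI half-width for a mean within-person change, in units of the SD of change, is t(0.975, n−1)/√n:

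- n = 20: 2.093/4.472 = 0.468
- n = 16: 2.131/4 = 0.533
- n = 12: 2.201/3.464 = 0.635

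The documents give no completer count, so 16 and 12 are assumptions. Twelve is 20 minus the eight participants in the 04.12.20 update of Section 7, whose in-person assessments were postponed ("Once the social distancing order will lift, we will collect face to face blood test and frailty assessments"), not stated as lost.

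**5. Why the measure must be named.** Section 8.6 defines non-frail as 0 characteristics and frail as at least 3, and states "Pre-frailty is defined as 1 or 2 of these characteristics". Of the five possible one-point improvements in score, 1→0 and 3→2 change status, while 2→1, 4→3 and 5→4 do not. Score and status can therefore give different answers.

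**The case against.** **Intervention could mean before versus after.** The plan does speak of the period from baseline to follow-up. But baseline frailty is an adjustment covariate, so it cannot also be an outcome row, and no time term, random effect or other within-person correlation is stated. This reading does not rescue the text.

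**It is a feasibility pilot, power analysis is expressly declined, and the model fails visibly.** Feasibility and the covariate main effects are indeed untouched. But the frailty effect is what the pilot is declared to supply for the next trial, so the gap matters.

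**Mean change is a preference.** The plan treats frailty as ordinal, and a t-interval on a bounded 0–5 score with 20 people is an approximation. This stands in part: what must be settled is that one within-person measure is named, and an ordinal alternative is acceptable. A longitudinal ordinal model may itself be unstable with 20 people, two time points and possibly sparse categories.

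**Some details are secondary.** The exact ranks depend on how many frailty and ethnic levels are observed; the aliasing does not. Home-kit HbA1c bears on HbA1c and not on frailty. Another group was due to finish in June 2020, so more than eight frailty assessments may have been deferred. These points are fair and do not alter the conclusion.

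**Group B was itself active.** It was to have one session, self-study modules, monthly calls and the same type of app. The lost contrast was therefore group versus abbreviated individual delivery, not intervention versus nothing. That is correct, and it makes the planned comparison narrower, not estimable.

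**Conclusion.** The concern holds, with high confidence. As written, Sections 12.3 and 12.4 cannot produce an intervention effect on the primary frailty outcome or on any secondary outcome. Nor can they test an interaction or supply the effect that Section 12.2 promises for a future sample size. The failure is structural and holds for any covariate values. The documents name the variable and the period (change in frailty category or score, baseline to follow-up), but give no summary measure, model, interval or test for it. With all 20 pairs complete, a mean change can be estimated to within about ±0.47 SD of change. That describes change; it cannot attribute it to the intervention. This must be corrected before frailty results are reported or used for planning.

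**What to change.** Amend Sections 12.3 and 12.4 to a single-arm, before-and-after analysis:

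- Delete the intervention and interaction terms.
- Name one governing primary measure: mean within-person change in frailty score (end of study minus baseline) with a 95% CI. If the team prefers to stay ordinal, use a longitudinal ordinal model with a time term and within-person correlation in its place, not in addition.
- Report the baseline-by-end table of frailty status, with any exact sign test of improved versus worsened, as supportive. That test needs at least six changers, all in one direction, for two-sided p < 0.05 (2 × 0.5⁶ = 0.031; five of five gives 0.0625).
- For HbA1c, fasting glucose, BMI, SPPB and PROMIS, report within-person change with a 95% CI.
- State that the analysis was specified after the control arm was dropped and Group A had finished. Describe results as uncontrolled change throughout, including in Section 12.2.
- Reconcile the statements in Sections 7 and 10.1 that the science was unaffected with the loss of the comparison.

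Optionally, add sensitivity analyses that set apart home-kit HbA1c (for HbA1c) and deferred assessments (for frailty), with the numbers stated.

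The cost is wording only; no new data are needed. The analysis must carry a post-hoc label, the conclusion is weaker (change, not effect), and any sensitivity analysis will be imprecise, for example ±0.64 SD if 12 remain (assumed).
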